Two cohorts will be constructed for the outcomes of interest (a malignancies cohort – for evaluating new malignancies as a composite outcome and for malignancies' sub-types; and a serious infections cohort – for evaluating serious infections outcomes), considering outcome-specific inclusion and exclusion criteria. In the main analysis, on-treatment definition of exposure will be considered: patients will be considered at risk while exposed to the first anifrolumab treatment (or the SOC treatment for the exposed to SLE SOC group). For the analysis of malignancy outcomes, follow-up will start after a 12-months latency period after the index date and an additional 12-months period at risk (off-drug) will be considered to capture outcomes that might occur after drug cessation.

Exposure variables

Patients exposed to anifrolumab will be defined by the initiation of anifrolumab (anatomical therapeutic chemical code L04AA51).

SLE SOC patients will be defined by the use of drugs indicated for moderate to severe SLE (in addition to antimalarials and/or low dose corticosteroids): medium to high dose corticosteroids, immunosuppressants (synthetic or biologics [except anifrolumab]), plasmapheresis or intravenous immunoglobulins.

Outcome variables

Primary outcomesCONFIDENTIAL AND PROPRIETARY16 of 130

Malignancies will be defined as the first coded diagnosis for haematological malignancies and solid tumours available in the data sources.

Serious infection will be defined as an infection leading to hospitalisation, use of intravenous antimicrobials or an infection-related death, operationalised as:

- Infections leading to hospitalisation: a) infection diagnosis as part of a hospitalisation episode or b) infection diagnosis in primary or secondary care settings up to 7 days before hospitalisation.
- Prescription/administration of intravenous antimicrobials.
- Infection-related death: recorded diagnosis of infection in primary or secondary care settings with record of death within the subsequent month.

Secondary outcomes

Specific types of malignancies: haematologic, solid and skin malignancies.

Serious infection components: infection leading to hospitalisation, infection requiring treatment with IV antimicrobials and infection-related death.

Serious infection types grouped as opportunistic serious infections, other serious infections, pneumonia (overall), fatal and non-fatal pneumonia (separately).

Exploratory outcomes

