The final study reports are planned¹ for 30 November 2028 for *serious infections outcomes* and for 30 November 2032 for *malignancy outcomes*, provided that required sample sizes are reached at that time. It is estimated that the required sample size of 1,312 anifrolumab users for the serious infections outcomes, and 3,195 anifrolumab users for the malignancies outcome (see Section 10.5.2) will be attained, under the assumption that anifrolumab uptake will increase during the study period from less than 1% to ~16% at the end of the study enrolment (see Section 10.5.1 and Table 27 for further details on the estimated number of annual anifrolumab users in each data source). However, these assumptions of anifrolumab uptake will be assessed at the progress report and the first interim report to confirm the milestones for the final study reports. The final study reports will include all descriptive, comparative, exploratory, sensitivity analyses and meta-analysis for all the data sources for the outcomes of interest.

¹ Assuming protocol approval by PRAC on 31st August 2023.

Table 1 Study milestones

Milestone	Planned date ^a
PRAC approval	31 August 2023 ^b
Registration in the EU PAS register	30 November 2023
Start of data collection ^c	31 May 2025
Interim report 1 (SI & M)	31 May 2027
Final report of study results (SI)	30 November 2028
Interim report 2 (M)	31 May 2030
End of data collection ^d	30 November 2031
Final report of study results (M)	30 November 2032

^aSchedule is dependent on the date of protocol approval by PRAC. Any deviations from this tentative date may lead to an amendment of all subsequent dates.

^bThis is a tentative date and will be revised to reflect actual date of approval if needed.

^cDate at which data extraction starts.

^dDate at which the analytical dataset is completely available.

Abbreviations: EU PAS - European Union electronic Register of Post-Authorisation Studies; PRAC - Pharmacovigilance Risk Assessment Committee SI - Serious Infections Outcomes; M – Malignancies Outcomes

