For a given matching ratio (exposed: non-exposed) and a given IR, simulations were carried out for a range of overall exposed sample sizes (total sample size of exposed patients across data sources). For each overall sample size (e.g., n = 3000 exposed patients), a proportion of the overall population (country-level sample size) was assigned to each data source (proportions are presented in Table 13). These proportions are based on estimated final sample sizes for the different data sources given the relative sizes of each data source and the prevalence of SLE in each study country. The SLE prevalence in each data source was obtained by literature review (see references in Table 13) The following steps were repeated 1,000 times to get 1,000 simulated 95% CIs for HRs.

Using the simsurv package, survival times were simulated for each data source from a Weibull distribution assuming proportional hazards. The average population-level treatment effect chosen was from a pre-specified list of values -1.5, 1.8 or 2 with assumed variances of SD(HR) = 0.1 and 0.2. The provided sample sizes were taken as the exposed sample size and the non-exposed sample size was calculated as matching ratio * country-level sample size. The average follow-up times were 2 years for serious infections and 5 years for malignancies.

The estimated data source level log(HRs) for exposure status, standard errors and 95% CI were computed by fitting a cox proportional hazards model to the simulated data. The data source level log(HRs) and their standard errors were entered in a random-effect meta-analysis model to compute the pooled HR and its 95% CI. The inverse-variance method was used with the R meta package.

Finally, the proportion of 1,000 simulated runs where the meta-analysis p-value < 0.05, representing the power, was computed. Power was estimated for each pre-specified sample size of exposed group under two different outcome-specific IRs and two allocation ratios (1:1 and 1:3) for three assumed average treatment effects, HRs – (1.5, 1.8 and 2) (Log(HR) values of 0.405, 0.588 and 0.693 in lognormal space respectively) with SD[HR)] – 0.1 (expressed as the geometric coefficient of variation of log(HR) - 0.066, 0.056, 0.05 for three HRs respectively) and 0.2 (expressed as the geometric coefficient of variation of log(HR) - 0.132, 0.11, 0.099 for three HRs respectively In addition, the exact sample size required to achieve 80% power was estimated (Table 13).

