	SD(HR) SD(HR) SD(HR) SD(HR) SD		SD(HR)	SD(HR)					
		=0.1	=0.2	=0.1	=0.2	=0.1	=0.2		
	500	0.265	0.256	0.474	0.516	0.621	0.617		
	1000	0.409	0.433	0.716	0.706	0.832	0.813		
	1500	0.520	0.500	0.813	0.779	0.897	0.902		
0.6 1000	2000	0.586	0.606	0.876	0.854	0.955	0.937		
9.6 per 1000 person-years	2500	0.662	0.644	0.905	0.893	0.958	0.955		
person-years	3000	0.714	0.657	0.930	0.908	0.976	0.972		
	3500	0.750	0.722	0.962	0.923	0.985	0.972		
	4000	0.800	0.753	0.965	0.941	0.985	0.974		
	4500	0.816	0.801	0.971	0.964	>0.999	>0.999		
39.8 per	500	0.583	0.569	0.852	0.829	0.943	0.925		
1000	1000	0.789	0.716	0.958	0.947	0.981	0.985		
person-years	1500	0.882	0.835	0.977	0.975	0.995	0.987		

Table 12 Meta-analysis level power to detect pre-specified target HR under different study size and assumptions of serious infections incidence – allocation ratio 1:3

Abbreviation - HR: hazard ratio; IR: incidence rate; SD: standard deviation

For the malignancy outcome, using an allocation ratio of 1:3, an average follow-up time of 5 years, and an IR of 6.31 per 1000 person-years, the minimum required sample size to achieve 80% power for detecting a pre-specified true HR of 1.5 (geometric mean of 0.425 in lognormal space) from an effect distribution with SD(HR) of 0.2 (geometric coefficient of variation of 0.132 in lognormal space), is approximately **3,195** anifrolumab patients across all countries.

For serious infections, using an allocation ratio of 1:3, an average follow-up time of 2 years, and an IR of 39.8 per 1000 person-years, the minimum required sample size to achieve 80% power for detecting a pre-specified true HR of 1.5 (geometric mean of 0.425 in lognormal space) from an effect distribution with SD(HR) of 0.2 (geometric coefficient of variation of 0.132 in lognormal space), is approximately **1,312** anifrolumab patients across all countries.

The proportional share for each data source was based on the expected number of SLE patients as presented in section 10.5.1. These proportions along with the required country-level sample size to achieve 80% power to detect a pre-specified HR of 1.5 (geometric mean of 0.405 in lognormal space) from an effect distribution with SD(HR) of 0.2 (geometric coefficient of variation of 0.132 in lognormal space) with a 1:3 matching is presented in Table 13.

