• Most malignancies have long latency periods in the absence of immunosuppression [66]. Although immunosuppression shortens the latency period [100], current study follow-up time may be short (seven years will be the maximum duration between first enrolled patient and the end of follow-up) to identify some malignancies. Thus, the incidence may be underestimated. However, haematological malignancies are expected to be the most frequent cancer types among SLE patients [12, 13, 84]. For those, latency periods are likely to be shorter.

• Previous research suggests that biologics are associated with an increased risk of malignancies [100]. Therefore, cancer screenings (e.g., for breast or cervical cancers) and closer surveillance may be reinforced among patients exposed to biologics, namely anifrolumab [16]. If so, anifrolumab patients may have a diagnosis at an earlier time point than it would have been if it had been diagnosed by its clinical appearance. This may result in an increased risk of malignancy in anifrolumab patients. However, patients exposed to SLE SOC may also be exposed to other biologics or known carcinogenic drugs (such as cyclophosphamide) which may result in similar adherence to cancer screenings, minimising surveillance bias [41].

Capturing malignancies using claims data may be prone to misclassification because unconfirmed cases may be captured. Since no population-based cancer registry is used for France (SNDS), Germany (SHI) and Spain (SIDIAP), misclassification may occur. Additionally, in France, malignancies are only captured for patients that were hospitalised. Although virtually all patients may be hospitalised at some stage of the disease, under-detection may occur.

SLE severity and activity

• Disease severity and activity scales (e.g., Systemic Lupus Erythematosus Disease Activity Index 2000 [SLEDAI-2K score]) are frequently used in randomised controlled trials but are not routinely recorded in secondary data sources and therefore were not included. Activity could also be addressed by considering specific biomarkers (e.g., C3, C4) which are unlikely to be systematically used and available. To minimise the lack of available data, severity and activity algorithms that were previously defined [39, 56] will be used, incorporating information that is used in routine practice: scale-up of SLE treatment strategies, SLE clinical manifestations and HRU.

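### The 80% power behind 1,312 and 3,195 exposed patients assumes mean follow-up of 2 and 5 years; the protocol's own dates, uptake and latency allow about 0.9–1.2 and 2.2–2.7 years, so power is about 60–70%

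*Protocol*

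**What the plan says.** Section 10.5.2 (Simulation steps) fixes the follow-up input: "The average follow-up times were 2 years for serious infections and 5 years for malignancies". The malignancy result is then stated as obtained "using an allocation ratio of 1:3, an average follow-up time of 5 years, and an IR of 6.31 per 1000 person-years", and serious infections (SI) likewise with 2 years and 39.8 per 1,000 person-years. Both are described as the "minimum required sample size to achieve 80% power for detecting a pre-specified true HR of 1.5" from an "effect distribution with SD(HR) of 0.2". Power is the simulated rejection rate: "the proportion of 1,000 simulated runs where the meta-analysis p-value < 0.05, representing the power, was computed".

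Other sections determine the follow-up that can accrue:

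- **Section 10.2.1, Table 3:** launches run from 11 March 2022 (Germany) to May 2023 (Spain, to be confirmed). Enrolment ends on 30 April 2025 (SI) and 31 May 2028 (malignancy). Follow-up ends on 31 May 2025 and 31 May 2029.
- **Sections 5 and 10.3.1.2.1:** for malignancy, "follow-up will start after a 12-months latency period after the index date".
- **Section 10.9:** for malignancy, "seven years will be the maximum duration between first enrolled patient and the end of follow-up".
- **Appendix 4.3, Table 27:** annual new initiators by source. France has 226, 310, 469, 860, 434 and 396 in 2023–2028.

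Section 7 plans the final reports for 30 November 2028 and 30 November 2032, "provided that required sample sizes are reached at that time". The re-checks in Sections 7, 10.4 and 10.5.2 concern uptake and patient numbers.

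**The concern.** Power for a hazard ratio depends on events, which are rate times person-time. A patient count implies 80% power only if each patient brings the assumed follow-up.

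A quick check shows the conflict. A mean of 2 years ending on 31 May 2025 needs a mean index date near 31 May 2023. A mean of 5 years after a 1-year latency, ending on 31 May 2029, needs the same date. Yet by the end of 2023 Table 27 has only 14 + 19 + 226 + 15 + 26 + 46 = 346 initiators. That is 24% of the 1,435 expected for SI and 10% of the 3,506 expected for malignancy. A patient enrolled on the last permitted malignancy date, 31 May 2028, completes latency on the day the study ends and contributes no time at risk.

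Both primary outcomes are affected. The planned checks could all be passed on headcount while the study holds far less information than its 80% statement implies.

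**Working it through.** **1. Reproducing the plan's figure.** Inputs are from Section 10.5.2 and Table 13: four sources with shares of 5.89%, 74.56%, 5.40% and 14.16%; 1:3 matching; HR 1.5; SD(HR) 0.2; λ = 0.0398 (SI) or 0.00631 (malignancy) per person-year.

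- Source-level log HR ~ N(0.405, 0.133²), where 0.133 = √ln(1 + (0.2/1.5)²).
- Events are binomial with probability 1 − exp(−λ·HR·f) in the exposed and 1 − exp(−λ·f) in comparators, where f is the mean follow-up.
- Each source gives a log rate ratio with variance 1/d₁ + 1/d₀ (d₁, d₀ = events). These are pooled by random-effects inverse variance (DerSimonian–Laird) and tested at two-sided p < 0.05, with 60,000 runs.
- The Weibull shape is not given, so a constant hazard is assumed.

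Result: 0.79 at 1,312 × 2 years and 0.79 at 3,195 × 5 years. Using REML, or centring on an arithmetic mean HR of 1.5, gives 0.78–0.80. The stated 80% is reproduced.

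**2. Follow-up the protocol allows.** Table 27 initiators are summed over sources, with 2022 counts shown as below 10 set to zero. Starts are spread evenly within each calendar year from launch, and the final year is pro-rated to the end of enrolment. Only the end of study censors.

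| Start year | SI: n × years = PY | Malignancy after latency: n × years = PY |
|---|---|---|
| 2022 | 29 × 2.78 = 81 | 29 × 5.78 = 168 |
| 2023 | 317 × 1.89 = 599 | 317 × 4.89 = 1,550 |
| 2024 | 460 × 0.91 = 419 | 460 × 3.91 = 1,799 |
| 2025 | 205 × 0.25 = 51 | 629 × 2.91 = 1,831 |
| 2026 | – | 953 × 1.91 = 1,822 |
| 2027 | – | 634 × 0.91 = 578 |
| 2028 | – | 200 × 0.21 = 41 |
| Total | 1,011; about 1,150 PY; mean 1.14 | 3,222; about 7,789 PY; mean 2.42 |

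Products use unrounded years.

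Two other placements bracket these means:

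- All final-year initiators placed inside the enrolment window (n = 1,435 and 3,506): 0.87 and 2.24 years.
- Everyone starting on the first possible day of each year, a ceiling: 1.22 and 2.69 years.

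If the 5 years were meant to run from index, the pro-rated malignancy mean is 2.42 + 1 = 3.42 years, still short.

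**3. Power at that follow-up**, by the method of step 1:

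| Scenario | SI | Malignancy |
|---|---|---|
| Stated N, pro-rated mean | 1,312 × 1.14: 0.68 | 3,195 × 2.42: 0.63 |
| Pro-rated N and mean | 1,011 × 1.14: 0.61 | 3,222 × 2.42: 0.64 |
| Stated N, lower mean | 1,312 × 0.87: 0.61 | 3,195 × 2.24: 0.61 |
| Expected N, ceiling mean | 1,435 × 1.22: 0.71 | 3,506 × 2.69: 0.68 |

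The other pooling variants shift these by about 2 points. Expected events, N[1 − exp(−1.5λf)] + 3N[1 − exp(−λf)], fall from 449 to 261 (SI) and from 445 to 218 (malignancy) at the stated N and pro-rated means.

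**4. Cross-check from the protocol's own tables** (HR 1.5, SD(HR) 0.2, 1:3), converting person-years to patients at the assumed follow-up and interpolating:

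- SI, stated N: 1,312 × 1.14 / 2 = 748. Table 12 gives 0.569 + (248/500)(0.716 − 0.569) = 0.64.
- SI, pro-rated N: 1,150 / 2 = 575, giving 0.59.
- Malignancy: 7,789 / 5 = 1,558. Table 10 gives 0.632 + (58/500)(0.694 − 0.632) = 0.64.
- Ceilings: 1,435 × 1.22 / 2 = 875 and 3,506 × 2.69 / 5 = 1,886, both giving 0.68.

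**The case against.** - **The end dates are provisional.** Section 10.2.1 expects them to differ by country, and Table 3 footnotes e and f say they need adapting. They rest on a two-year data lag, while Table 7 lists 2–13, 12, 12 and 6 months (Section 10.4.1.3 gives 15–16 months or more for Germany). Extending the study period is a named mitigation. Moving the SI end 12 months later with enrolment unchanged would add up to a year per patient and bring the mean to about 2. This stands as a condition on the figures. The same step takes malignancy only to about 3.4 years, and Sections 5 and 10.1 state the 2025 and 2029 dates plainly.
- **The SI rate may be conservative.** The 39.8 per 1,000 counts hospitalisation with infection as primary diagnosis in newly diagnosed SLE, whereas the study outcome is broader and the population more active. A higher rate would offset some lost person-time. The documents do not say how much.
- **Comparators may be followed longer,** because their index date is set on time since standard-of-care start. Giving them 1.6 and 3.1 years (assumed) against 1.1 and 2.4 for the exposed yields only 0.69 and 0.64.
- **Larger effects remain detectable.** At 575 and 1,558 patient-equivalents, Tables 12 and 10 give about 0.85 and 0.90 for HR 1.8. This is true, but the headline claim is for HR 1.5.
- **The limitation is partly disclosed.** Section 10.9 says malignancy follow-up may be short, but draws only the consequence of underestimated incidence.

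A reader might also infer three stronger things. First, that 1.1 and 2.4 years are maxima: they are pro-rated estimates, and the ceilings are 1.22 and 2.69. Second, that follow-up alone cuts SI person-time to 44% of plan (1,150 / 2,624) and power to about 0.61: that also removes about 420 patients through pro-rating, while follow-up alone leaves 1.14 / 2 = 57% and power of about 0.68. Third, that reports issue as soon as a headcount is met and a null result will be misread: the reports have fixed dates conditional on sample size, and hazard ratios with 95% CIs will show the imprecision.

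**Conclusion.** The contradiction holds. The follow-up inputs in Section 10.5.2 cannot be met under Table 3, Table 27 and the 12-month latency, even if every patient starts on the first possible day of each year and nobody stops treatment, dies or leaves. At the assumed rates, HR 1.5, SD(HR) 0.2 and 1:3 matching, power is about 60–70% instead of 80%, ranging from about 0.61 to 0.71 for SI and from 0.61 to 0.68 for malignancy. At 1.1 and 2.4 years, about 80% would need roughly 2,600 exposed patients (SI) and 7,000–7,500 (malignancy).

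These values assume a constant hazard, equal follow-up in both groups, the end dates as written and the protocol's background rates. Later end dates or a higher SI rate could recover some power. On-treatment censoring, which was not modelled, would reduce it, most directly for SI, which has no additional 12-month off-drug window.

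**What to change.** 1. Re-run the existing simulation with staggered entry from Table 27, the Table 3 dates (or the country-adapted dates once set), the 12-month malignancy latency and on-treatment censoring.
2. In Sections 5 and 10.5.2, replace the 80% power statements with the delivered power, or with the hazard ratio detectable at 80%. Amend the required sample sizes that Section 7 relies on to match.
3. Add accrued exposed person-years or events to the planned checks of uptake and patient counts. The plan's own targets equal 1,312 × 2 = 2,624 (SI) and 3,195 × 5 = 15,975 (malignancy) exposed person-years.

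The cost is one re-run of an existing simulation and a wording change. The stated power becomes less favourable, and the case for using the named mitigations may arise sooner.

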10.5 Study size

10.5.1 Expected number of SLE patients exposed to anifrolumab

Due to the recency of anifrolumab approval in the EU (14 February 2022), data on its uptake in the selected data sources for the duration of the study enrolment period (up to April 2025 for serious infections, and May 2028 for malignancies) is not available. Therefore, estimates of the number of expected anifrolumab patients in each data source for each year of the study were made based on country-level assumptions of the prevalence of SLE, proportion of patients with moderate to severe SLE, proportion of patients who have non-renal SLE, proportion of non-renal SLE

patients who are treated, a gradual uptake of anifrolumab from 1% in the initial years after market approval to 13-16% in 2028 and population coverage of each selected data source. Details of these assumptions and the annual number of exposed patients in each data source are provided in Appendix 4.3. Number of SLE patients exposed to anifrolumaband Table 27.

The average number of patients with SLE expected to be identified in the data sources every year (potential pool of comparators) and the total number of new patients exposed to anifrolumab identified during the enrolment period in each study cohort and data source are summarised in Table 8. For the serious infections and malignancies' cohorts, 1,435 and 3,506 patients newly exposed to anifrolumab may be captured, respectively⁸.

Table 8 Expected size of the SLE population exposed to anifrolumab in the selected data sources

Country data	Average number	Expected number of patients initiating anifrolumab				
Country, data source	of SLE patients per year ^a	Malignancies' cohort (Enrolment: 2022-2028)	Serious infections' cohort (Enrolment: 2022-2025)			
Denmark, National Registers	1,122	183	89			
France, SNDS	15,501	2,695	1,005			
Germany, SHI	1,224	216	126			
Spain, SIDIAP	2,944	412	216			
All		3,506	1,435			

Abbreviations - SHI: Statutory Health Insurance; SIDIAP: System for the development of primary care research database; SLE: systemic lupus erythematosus; SNDS: National Health Data System

^aEstimated as the annual average number of patients in each data source with moderate to severe, non-renal SLE treated with SLE SOC for the period 2022 to 2028 (more details in Appendix 4.3. Number of SLE patients exposed to anifrolumab).

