Considering the estimated number of patients initiating anifrolumab during the study period (3,506 for the malignancies cohort, and 1,435 for the serious infections cohort Table 8) and the required sample size presented above (3,195 for the malignancies cohort and 1,312 for the serious infections

cohort), there is a reasonable assumption that the final study report milestones as specified in this protocol can be met. However, the assumptions used in the calculation of the exposed anifrolumab patients will be evaluated at the first progress report (31 May 2026) and first interim report (31 May 2027). If the assumptions do not hold, the final study report milestones will be re-evaluated, and potential mitigation steps will be explored.

each data source)											
Country	Share of	Minimum required sample size	Minimum required sample size								
	country in	(anifrolumab patients) for the	(anifrolumab patients) for the SI								
	study (%)	Malignancy outcome with IR = 6.31	outcome with IR = 39.8 per 1000 py								
		per 1000 py									
Denmark	5.89%	188	77								
France	74.56%	2,382	978								
Germany	5.40%	173	71								
Spain	14.16%	452	186								
Total	100.00%	3,195	1,312								

Table 13 Minimum sample size needed for malignancy and SI outcomes (overall and in each data source)

Abbreviation - HR: hazard ratio; IR: incidence rate; SD: standard deviation

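### Table 13 has the Denmark and Germany rows exchanged, so four country-level minimum sample sizes are wrong; the overall minima and pooled power are not affected

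*Protocol*

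**What the plan says.** Section 10.5.2 of the protocol sets an overall minimum of 3,195 anifrolumab patients for malignancy and 1,312 for serious infections, then allocates each total to the four data sources in Table 13. The basis for the allocation is stated just before the table: "The proportional share for each data source was based on the expected number of SLE patients as presented in section 10.5.1".

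Table 8 in section 10.5.1 gives, for each source, the average number of SLE patients per year, then the expected initiators in the malignancy and serious infection cohorts:

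- "Denmark, National Registers 1,122 183 89"
- "France, SNDS 15,501 2,695 1,005"
- "Germany, SHI 1,224 216 126"
- "Spain, SIDIAP 2,944 412 216"

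Table 13 gives, for each country, the share, then the malignancy and serious infection minima:

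- "Denmark 5.89% 188 77"
- "France 74.56% 2,382 978"
- "Germany 5.40% 173 71"
- Spain: 14.16%, 452 and 186

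**The concern.** By the stated basis, the source with more SLE patients must have the larger share. Table 8 puts Germany above Denmark (1,224 against 1,122), whereas Table 13 gives Denmark the larger share and Germany the smaller.

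Table 13 presents its rows as the minimum needed in each data source, and a reader will naturally set them against the expected numbers in Table 8. On the printed rows, Denmark appears unable to reach its malignancy minimum (183 expected against 188), and Germany's requirement is understated for both outcomes.

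**Working it through.** **Inputs.** SLE patients per year (Table 8): Denmark 1,122, France 15,501, Germany 1,224, Spain 2,944. Overall minima (section 10.5.2): 3,195 and 1,312.

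**Step 1: shares.** The sum is 1,122 + 15,501 + 1,224 + 2,944 = 20,791. Share = country count / 20,791.

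| Country | Calculation | Share | Table 13 |
|---|---|---|---|
| Denmark | 1,122 / 20,791 | 5.40% | 5.89% |
| France | 15,501 / 20,791 | 74.56% | 74.56% |
| Germany | 1,224 / 20,791 | 5.89% | 5.40% |
| Spain | 2,944 / 20,791 | 14.16% | 14.16% |

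France and Spain reproduce to two decimals, which confirms that the Table 8 counts were used. Denmark and Germany reproduce only when exchanged.

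**Step 2: minima.** Minimum = share x overall minimum. The printed minima follow the printed shares: 5.89% x 3,195 = 188.2 and 5.40% x 3,195 = 172.5; 5.89% x 1,312 = 77.3 and 5.40% x 1,312 = 70.8. The exchange therefore runs through both rows and is not one mistyped cell. With the shares on the right rows:

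| Country | Malignancy, corrected (printed) | Serious infection, corrected (printed) |
|---|---|---|
| Denmark | 173 (188) | 71 (77) |
| France | 2,382 (2,382) | 978 (978) |
| Germany | 188 (173) | 77 (71) |
| Spain | 452 (452) | 186 (186) |
| Total | 3,195 | 1,312 |

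On rounding: the unrounded Danish share gives 172.4, but the table was evidently built from two-decimal shares, and 5.40% gives 172.5, printed as 173. Using 173 keeps the column total (173 + 2,382 + 188 + 452 = 3,195); 172 would make it 3,194.

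**Step 3: other possible bases.** Shares by expected malignancy initiators are Denmark 183/3,506 = 5.22% and Germany 216/3,506 = 6.16%. Shares by expected serious infection initiators are 89/1,435 = 6.20% and 126/1,435 = 8.78%. Neither gives the printed values. In every year of Table 27 Germany's SLE count exceeds Denmark's (for example 1,229 against 1,110 in 2022 and 1,219 against 1,133 in 2028), so no single year explains them either.

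**Step 4: comparison with expected initiators (Table 8).**

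| Country, outcome | Expected | Printed minimum | Corrected minimum |
|---|---|---|---|
| Denmark, malignancy | 183 | 188 (5 short) | 173 (10 above) |
| Germany, malignancy | 216 | 173 (43 above) | 188 (28 above) |
| Denmark, serious infection | 89 | 77 (12 above) | 71 (18 above) |
| Germany, serious infection | 126 | 71 (55 above) | 77 (49 above) |

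The only comparison that changes direction is Denmark for malignancy.

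**Step 5: pooled power.** As section 10.5.2 describes the simulation, each scenario applies one incidence rate, one distribution of hazard ratios, one matching ratio and one average follow-up to every source. The sources differ only in size. Exchanging Denmark and Germany leaves the same set of malignancy sizes (173, 188, 452, 2,382), so the pooled power is the same by construction.

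**The case against.** The strongest reply is that nothing of substance depends on these rows. Power is defined at the meta-analysis level, section 7 states the targets as totals, and section 10.5.2 bases its feasibility claim on totals (3,506 expected against 3,195; 1,435 against 1,312). The country figures are a pro-rata split. That is right, and it limits the point to a correction of the table. It does not make the printed figures correct: they contradict their own stated basis and create a Danish shortfall that the protocol's numbers do not support.

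It could also be said that the simulation steps in section 10.5.2 describe the shares differently, as resting on source size and SLE prevalence. The exact match for France and Spain shows that the Table 8 counts were used, so this does not explain the other two rows.

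Three stronger readings are tempting but not supported:

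- A reader might infer that the power results or the overall minima are affected. They are not, for the reason in step 5 of the working.
- A reader might infer that a country below its Table 13 row would trigger mitigation at the 2026 and 2027 checks. The protocol says those checks concern the uptake assumptions, and section 10.4 links mitigation to whether the selected sources supply the required sample size. No country-level trigger is stated.
- A reader might take Spain (412 expected against 452) as a second error. Spain's row is correct. Expected initiators need not follow SLE-count shares, because assumed uptake differs by country. France's surplus of 2,695 - 2,382 = 313 more than covers Spain's 40, and the protocol claims only that the totals will be met.

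**Conclusion.** The point holds as a minor arithmetic correction. Two shares and four minimum sample sizes in Table 13 sit on the wrong rows: Denmark is overstated by 15 for malignancy and 6 for serious infections, and Germany is understated by the same amounts. The one visible consequence is that Denmark appears 5 patients short for malignancy when, on the stated basis, it is 10 above. Germany meets its minima under either version, and neither country is short for serious infections.

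The conclusion rests on the basis stated in section 10.5.2 and on the Table 8 counts. That pooled power is unchanged rests on the simulation having been run as described, with sources differing only in size.

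**What to change.** Exchange the figures of the Denmark and Germany rows in Table 13:

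- Denmark: 5.40%, 173, 71
- Germany: 5.89%, 188, 77

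The France and Spain rows and the totals of 3,195 and 1,312 stay as they are. The cost is six table cells; no simulation needs to be repeated.

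Optionally, add a sentence under the table saying that the country minima are a pro-rata split of the overall requirement and that only the overall total is expected to be met, so that Spain's 412 against 452 is not misread.
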